The two-day training developed by Drs. [name], [name] and [name] will be informed by previous staff training in community clinics using the ACP guide and brief counseling framework. The session will take place in a central location and will include discussion of roles and responsibilities of the health coach for this project, and a review of the counseling framework. Skill-building will focus on brief education and coaching to facilitate patients' setting health goals and creating highly specific and easily achievable action plans. Training will also include skill building in motivational interviewing, clear communication and use of health literacy best practices (slowing down, using plain language, reducing numeracy demands, pointing out key messages in the guide book and using teach-back to confirm understanding). The theory-based training is designed to improve health coaches' capacity to enhance patients' understanding of their disease and problem-solving ability to change their health behavior and adhere to their action plans. The training will also focus on effective telephone counseling and follow up, employing strategies developed in previous research to reach patients by phone. Instruction will also be provided on use of a tracking system to recorded number of contacts (phone and in person), length of time spent in each contact, number of attempts to reach patients, and the content of each session.

Nurse training will cover an overview of the usual care diabetes materials in the enhanced usual care arm only (the "Living Well with Diabetes: a self-care workbook"). A review of the standards for usual care delivery will be provided to avoid contamination, as well as training on the tracking system. This will be provided by the Director of Research for the family medical centers in collaboration with the study team.

Randomization. After the initial phone call to recruit participants, the RA will assign patients interested in participating to either the intervention or to the enhanced usual care arm based on an allocation table created prior to study recruitment using a simple 1:1 randomization scheme, stratified by site. Patients will receive a \$30 Walmart gift card at baseline, a \$30 Walmart gift card at 3 months and a \$30 Walmart gift card at 6 months for their participation. If the patient has a phone call for the 3 month follow-up, they can get their gift card the next time they come into clinic

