Baseline characteristics and demographics will be summarized overall and by clinic using descriptive statistics (mean \pm standard deviation for continuous variables, frequencies and percentages for categorical variables, and medians/quartiles as appropriate for ordinal variables). Analyses across all relevant outcomes (i.e., those corresponding to H₁-H₆) will mirror one another in general, with primary outcome being defined as HbA1c levels at six months. Secondary outcome measures include disease and treatment knowledge scores, self-efficacy scores, adherence to self-care behaviors, diabetes-related distress, diabetes-related quality of life and other clinical outcomes (blood pressure, LDL, cholesterol, BMI). Survey data will be collected at baseline, 3 and 6 months; clinical data will be collected at baseline, 3, 6, 9, and 12 months. The primary time point of interest for H₁-H₅ is three-month follow up and for clinical outcomes (H₆) is six-month follow-up, but subjects will be followed through 12 months in order to examine sustainability. We will assume missing data are missing at random, and analyses will consist of parametric statistical tests. Relevant statistical assumptions will be assessed as appropriate, and nonparametric analyses and/or transformations of variables will be explored in the event of violations.

Aim 1 analysis for each outcome will consist of an analysis of covariance (ANCOVA) in which overall mean (μ) follow-up outcome (e.g., HbA1c at 6 months) across groups will be modeled as follows:

$$\mu_i = \beta_0 + \beta_1 I(ACP intervention_i) + \beta_2 (Baseline_i) + \epsilon_i,$$

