where *i* corresponds to the individual subject (*i*=1,...,*total N*), β_0 serves as an intercept, β_1 serves as the intervention effect [*I*(*ACP intervention*_i) is an indicator variable for active ACP intervention arm], β_2 represents the effect of baseline value of the corresponding outcome variable, and ϵ_i represents random error. Primary analyses will test the null hypothesis H_0 : $\beta_1 = 0$ against the twosided alternative at the 5% level of significance. Similar analyses will be employed for all relevant outcomes at three and/or six-month follow-up (to examine efficacy/effectiveness) and 12-month follow-up (to examine sustainability). Baseline variables (demographics, comorbidities, health literacy, etc.) will be explored one at a time, in turn, for association with outcome(s), and where appropriate, models will adjusted for significant baseline prognostic variables. Exploratory analyses will employ linear mixed effects models that include a fixed treatment arm, baseline value, relevant prognostic variables, and time effects along with a random subject effect in order

to account for within-subject association among outcome observations. Exploratory analyses will involve inclusion of a fixed change-point or spline term(s) to examine changes in slope over different time periods and/or higher order/interaction terms. In order to examine whether there may a difference across clinic, a random clinic effect will be examined as well, and where appropriate, subgroup analyses by clinic will be employed.

To address Aim 2 (H₇), the subjects will be classified by literacy level (lower literacy or higher literacy), and above analyses will be repeated within each arm but include an indicator for literacy group. Further, the primary model (above) will be modified to include a literacy level effect and corresponding arm-by-literacy level interaction term.

To address Aim 3, we will analyze only those subjects randomized to the ACP intervention arm. We will examine association of (a) number of contacts with each subject and (b) length of contact time, with each relevant outcome variable (H_1 - H_6) at follow-up via a linear model as above. Each model will include an intercept, baseline value for the relevant variable, and variable (a) and/or (b), along with any additional demographics/prognostic variables found relevant in Aims 1 and 2.

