Analyses will follow an intent-to-treat (ITT) principle in which all subjects enrolled in the study, regardless of adherence to the study protocol, will be analyzed according to the arm to which they were randomized. Sensitivity analyses will involve the "as treated" dataset. Additional sensitivity analyses will examine multiple imputation methods such as: "best-case", "worst-case", null scenario, and propensity score methods. These multiple imputations will result in no less than five imputed datasets from which we may obtain at least five overall parameter estimates with corresponding standard errors. From these, we will estimate an overall average for all primary and secondary outcomes with appropriate standard errors to determine whether overall conclusions are sensitive to these missing data.⁴² In cases where data may not be assumed MAR (i.e., we suspect non-ignorable missingness), we will explore pattern mixture models and/or selection modeling to conduct further sensitivity analyses.

Power and Sample Size Considerations

Power and sample size calculations were based on primary outcome of HbA1c at six months, assuming an independent two-sample t-test, type I error rate of 5%, and equal variances across arms (1.9, according to previous data). Note that primary outcome analyses will employ ANCOVA, and as a result, the power calculations presented here are considered conservative since we anticipate the inclusion of baseline values in ANCOVA to result in better precision in estimating an intervention effect. We plan to enroll 750 subjects, with minimal anticipated dropout: 90% retention at six months (n= 675, 337 per arm) and 84% retention at 12 months (n=630, 315 per arm). For our primary outcome at 6 months, we will be able to detect a clinically meaningful difference in HbA1c across arms of \geq 0.43 with 80% power. With sample size set by the primary outcome of HbA1c at 6 months, we also present differences we will be able to detect with at least 80% power for the secondary clinical outcome of systolic blood pressure and for the subgroup analyses.

Qualitative provider/clinic barriers and facilitators to implementation

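### Site, the randomisation stratum, is missing from the primary ANCOVA, and models adjusted for screened covariates have no stated status beside it

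*Combined protocol and SAP*

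**What the plan says.** All references are to the combined protocol and SAP.

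- **Randomization paragraph:** patients are allocated "using a simple 1:1 randomization scheme, stratified by site". Study Sites gives six clinics. No blocks are mentioned.
- **Data Analysis, general paragraph:** HbA1c is the lead outcome, "with primary outcome being defined as HbA1c levels at six months".
- **Data Analysis, Aim 1:** one equation is written out, with an intercept, an arm indicator, the baseline value of the outcome and an error term. The primary analyses test the arm coefficient "against the twosided alternative at the 5% level of significance".
- **Same paragraph, next step:** "Baseline variables (demographics, comorbidities, health literacy, etc.) will be explored one at a time, in turn, for association with outcome(s". Then, where judged appropriate, "models will adjusted for significant baseline prognostic variables". This comes before the sentences labelled exploratory.
- **Clinic:** it appears only as a random effect to be examined, and in possible subgroup analyses by clinic, directly after the exploratory mixed models.
- **Aim 2 text:** it refers back to the written model as the primary one and adds a literacy term and an arm-by-literacy interaction to it.
- **Aim 3 text:** its models reuse whatever covariates Aims 1 and 2 found relevant.

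**The concern.** There are two separate issues.

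**Site.** A trial that randomises within sites would normally analyse with site in the model. The protocol itself rejects clinic-level randomisation partly because the practices differ so much, so it expects site differences. Leaving site out puts that variation into the error term.

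**Screened covariates.** The plan allows a second estimate of the treatment effect, adjusted for variables picked by their association with the outcome in the trial's own data. Four things are not stated: the significance threshold, the full candidate list, what makes adjustment appropriate, and whether the adjusted result may stand in for the written model. Nothing says that the screening is done without sight of arm. If the two estimates disagreed about significance, the text would not plainly settle which one to report as the trial's result.

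**Working it through.** **1. The plan's own figure.** Power and Sample Size Considerations assumes a two-sample t-test at 5%, a spread of 1.9, and 337 per arm at six months, and states "0.43 with 80% power". The detectable difference is (1.960 + 0.842) × SD × √(2/n).

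- 1.9 as SD, n = 337: 2.802 × 1.9 × 0.0770 = 0.410
- 1.9 as SD, n = 315 (the 12-month number): 0.424
- 1.9 as variance (SD 1.378), n = 337: 0.297

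The stated 0.43 is not reproduced exactly. It lies close only if 1.9 is an SD. The gap is on the conservative side and does not affect this point. SD 1.9 is used below.

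**2. Cost of omitting site.** Assumed, because the documents give neither: baseline–outcome correlation 0.5, and site carrying 5% of outcome variance beyond baseline.

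- SE reported without site: 1.9 × √(1 − 0.25) × √(2/337) = 0.1268
- SE with site: 1.9 × √(0.75 − 0.05) × √(2/337) = 0.1225

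If allocation is balanced within site, the true sampling SE is 0.1225 whether or not site is in the model. Omitting site then only overstates the SE:

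- Power without site = Φ((δ − 1.96 × 0.1268)/0.1225)
- Power with site = Φ(δ/0.1225 − 1.96)

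| Difference | Without site: formula (simulated) | With site: formula (simulated) |
|---|---|---|
| 0.30 | 66.3% (66.8%) | 68.8% (69.0%) |
| 0.43 | 93.1% (93.1%) | 94.0% (93.9%) |

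The simulation used 674 patients, six equal sites and 4,000 runs per scenario. It also included 15 candidate covariates, 5 of them prognostic (correlation 0.15 each).

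Type I error without site, by formula, is 2Φ(−1.96 × 0.1268/0.1225) = 4.2% at a 5% site share. At a 10% share the SE with site is 0.1180 and the result is 3.5%. Simulated values at site shares of 1%, 2%, 5% and 10%:

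- without site: 4.9%, 5.5%, 4.7%, 3.6%
- with site: 5.1%, 5.8%, 5.7%, 5.1%

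Monte Carlo standard error is about √(0.05 × 0.95/4000) = 0.34 points.

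If allocation is not balanced within site, the test without site is not conservative (5.2%, against 5.3% with site, at a 5% share). The loss is then in the estimate itself. Its simulated SE falls from 0.1274 to 0.1242 when site is added, a variance ratio of (0.1242/0.1274)² = 0.95.

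**3. Effect of screening under no treatment effect.** Screening at p < 0.05 is assumed. The Covariates paragraph lists about 12 candidates: six socio-demographic, social support, four health-status items and literacy.

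| Simulation | Written model always | Screened model always | Whichever of the two is significant |
|---|---|---|---|
| 12 candidates, 4 prognostic, 6,000 runs | 4.6% | 4.5% | 6.3% |
| 15 candidates, 5 prognostic, site share 1–10% | 3.6–5.5% | 3.5–5.3% | 5.0–7.2% |
| 15 candidates, none prognostic, site share 2% | 4.3% | 4.4% | 4.5% |

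A fixed screening rule that ignores arm therefore does no harm to type I error. The rise comes from choosing between two results, and only when some candidates are truly prognostic. In the second row's setting the two estimates differed with an SD of about 0.05 HbA1c points. The 95th percentile of the absolute difference was about 0.10, against a planned difference of 0.43.

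**The case against.** The strongest reply is that the plan does fix a primary model. It writes out one equation, ties the 5% test to that equation's arm coefficient, and later refers back to it as primary. The power section expects its gain in precision from baseline values and mentions no other covariate. Adjusted models are most naturally read as supplementary. This largely stands. A reader might infer that the primary estimate is left open altogether, and the documents do not support that. What remains is that the adjustment sentence precedes the text labelled exploratory, speaks of models in general, and never says that an adjusted result cannot replace the written one.

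A reader might also infer that screening inflates type I error. The simulations show that it does not. The 5–7% needs selective reporting, which the plan does not propose.

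On site, clinic is not ignored, since a random clinic effect is to be examined. Patients are individually randomised, so omission causes no bias, and the gain at 0.43 is under one percentage point of power. All of that stands. It limits the size of the point, but it is no reason to leave the stratification factor out of the primary model.

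Finally, deleting the screening outright would leave Aim 3 without its covariates. Aim 3 is a non-randomised comparison within one arm, where adjustment matters more. That also stands, and the fix allows for it.

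**Conclusion.** The point holds in a modest form. The primary ANCOVA omits the factor used to stratify randomisation, and the plan gives no status to models adjusted for covariates chosen by screening.

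The site omission costs precision, not validity: about two points of power at a 0.30 difference and about one at 0.43. If allocation is balanced within site and site effects are large, the test is also slightly conservative (about 3.5% at a 10% site share). These sizes rest on an SD of 1.9, a baseline correlation of 0.5 and the assumed site share.

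The undefined status of the adjusted models could, at worst, move type I error from 5% to about 5–7%. That assumes 12–15 candidates of which 4–5 are prognostic, screening at p < 0.05, and reporting of the more favourable of two models. It describes what the wording leaves possible, not what the sponsor intends.

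**What to change.** 1. State that the single primary model for six-month HbA1c is arm + baseline HbA1c + site, with site as a fixed effect.
2. Name any further covariates for that model now. The list need not be the same for every outcome.
3. Label every model with screened covariates as supportive or exploratory, and say that it cannot replace the primary estimate.
4. Name the Aim 3 adjustment covariates in advance instead of carrying over whatever the screening selects.
5. State whether allocation is blocked within site. This determines whether omitting site costs precision or makes the test conservative.

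The cost is a few sentences in the Data Analysis section, one in the Randomization paragraph, and five degrees of freedom (six sites less one) out of about 670. No new data are needed, because site and the listed covariates are already recorded.

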[name], former Assistant Secretary of DHHS, has proposed a Health Literate Care Model based on the chronic care model.^{30,31} The model encourages both patients and providers to be activated and engaged and suggests that improving health outcomes relies on patients' full engagement. Our strategy, in combination with PCMH standards achieved by each clinic, and previous clinic training by [name] in implementing health literacy strategies recommended in the Agency for Health Care Quality and Research's (AHRQ) Health Literacy Universal Precautions Toolkit³² address many of the attributes included in this model: 1) assuming all patients are at risk of not sufficiently understanding their disease or self- management; 2) providing clear communication following plain language principles and easy to read, culturally appropriate materials, 3) confirming and ensuring patients understand via the '*teach back*' technique, 4) providing close follow-up with patients using a health coach, 5) incorporating provider health literacy training and point-of-care clinical reminders for medication reviews, 6) use of an electronic health record (EHR) to track progress. *We will use health coaches to ensure constant patient engagement and provide the tools necessary to frequently monitor action plans and performance.*

Hypothesis and/or Specific Aims or Objectives

The primary aims and hypotheses are to:

1. Test the effectiveness of the ACP diabetes health literacy intervention to improve a range of diabetes-related outcomes among rural patients.

Compared to enhanced usual care, patients receiving ACP intervention will demonstrate:

- H_1 greater disease and treatment knowledge H_2 higher self-efficacy to manage diabetes H_3 greater adherence to self-care behaviors H_4 less diabetes-related distress H_5 improved diabetes-related quality of life H_6 better disease control (HbA1c, blood pressure)
- 2. Compared to usual care, evaluate whether the intervention reduces disparities by patient literacy level.

H₇ Limited health literacy will be associated with the above health outcomes in the enhanced usual care arm, but not in the intervention arm.

[figure not shown]
- 3. Investigate whether a threshold or gradient effect exists between the amount of follow-up counseling (number of action plans) and intervention effectiveness.

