- 4. Determine the fidelity of all intervention components, and explore any identified patient, provider (physician, nurse, health coach), and/or health system barriers to implementation.
- 5. Assess the costs associated with implementing the ACP intervention from a health system perspective.

Study Design and Procedures

We will conduct a 2-arm, patient-randomized, pragmatic trial among 750 patients in Arkansas with type 2 diabetes to test the effectiveness and fidelity of a multifaceted, health coachled, low literacy, self-management intervention to improve behavioral and clinical outcomes compared to enhanced usual care in level 3 patient centered medical homes. Enhanced usual care differs from standard diabetes care because enhanced usual care includes patient resources associated with PCMH (team-based care, electronic health records, and care coordination). Eligible, consented patients will be followed for 1 year post baseline interview. Those receiving the ACP intervention will be administered the ACP health literacy strategy at baseline, with 'frontloaded' telephone or in-person follow-up education approximately every 3 months, counseling and action-planning occurring at approximately 2 weeks, 4 weeks, and 8 weeks and then monthly between guarterly clinical visits. In-person, 'point-of-care' counseling sessions will occur guarterly, coinciding with diabetes routine clinical visits. We intentionally aimed to optimize the number of 'touch points' over 1 year, taking into account a reasonable workload for health coaches. Addressing Aim 3, which seeks to ascertain the minimum number of action plans necessary to achieve clinical diabetes goals, or an increasing benefit is seen with more touch points (no threshold). Primary outcomes include intermediary biomarkers indicative of proper disease selfmanagement (HbA1c, blood pressure, LDL cholesterol). In addition, secondary outcomes to be measured include diabetes and treatment-related knowledge, self-efficacy, disease-related distress and quality of life, activation, health behaviors and health services utilization. To determine the reliability and costs associated with delivering the intervention, we will also closely monitor the implementation process and evaluate the fidelity of the components and strategies.

		hanced Usual Care and Intervention
	STANDARD	DIABETES MEDICAL CARE
		In Both Arms
Care Management	of medical care	rting
		AND SELF-MANAGEMENT SUPPORT
	'Enhanced" Usual Care Arm	Intervention Arm

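### Aim 3 asks whether the dose relation is a threshold or a gradient, but its listed model names no analysis of dose shape and on its natural reading gives only a slope

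*Combined protocol and SAP*

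**What the plan says.** The aim is stated twice in the combined protocol and SAP. Under Hypothesis and/or Specific Aims or Objectives, Aim 3 reads "Investigate whether a threshold or gradient effect exists between the amount of follow-up counseling (number of action plans) and intervention effectiveness". Study Design and Procedures adds that Aim 3 seeks the "minimum number of action plans necessary to achieve clinical diabetes goals, or an increasing benefit is seen with more touch points (no threshold").

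The analysis is in the Aim 3 paragraph of Data Analysis. It is restricted to the ACP arm: "We will examine association of (a) number of contacts with each subject and (b) length of contact time, with each relevant outcome variable", through a linear model that refers back to the Aim 1 model. The terms follow: "Each model will include an intercept, baseline value for the relevant variable, and variable (a) and/or (b"), plus any demographic or prognostic variables found relevant in Aims 1 and 2. Nothing further is specified for dose.

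Two other sentences in Data Analysis could bear on shape. The exploratory analyses, described before the Aim 2 and Aim 3 paragraphs, allow "inclusion of a fixed change-point or spline term(s) to examine changes in slope over different time periods and/or higher order/interaction terms". The general paragraph on assumptions says "nonparametric analyses and/or transformations of variables will be explored in the event of violations".

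**The concern.** The question is about shape and the listed model is not. A slope on number of contacts says whether patients with more contacts tend to have better outcomes. It does not say whether the benefit appears at some number of contacts or builds up steadily, and it gives no minimum number. If the shape is examined only after the data are seen, a reported threshold would depend on a choice that nothing in the plan constrains.

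The exposure also changes between aim and analysis. The aim counts action plans; the analysis counts contacts and minutes. A contact need not produce a new action plan, because the follow-up calls in the Figure 1 table may instead review progress or solve problems with an existing one. The Aim 3 paragraph does not say that contacts stand in for action plans.

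At stake is a stated aim that bears on how many touch points the intervention needs, which Study Design and Procedures links to coach workload.

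**Working it through.** **1. Aim against model.**
- Asked: threshold or gradient, and the minimum number of action plans.
- Listed for Aim 3: intercept, baseline value, contacts and/or contact time, covariates.
- Not named for dose: categories, a cut-point, a spline or change-point, a departure test, or a rule for naming a minimum.
- The change-point and spline terms are for slope over time periods. The higher-order and interaction terms name no variable. The transformations depend on violated assumptions.

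**2. Two shapes, one slope.** The Follow-Up row of the Figure 1 table schedules, up to month 6, calls at 2, 4 and 8 weeks, visits at months 3 and 6, and calls at months 4 and 5: 3 + 2 + 2 = 7 contacts. Assume patients are spread evenly over 0 to 7 contacts. The mean is 3.5 and the variance is (8² − 1)/12 = 5.25.

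- Step of height h at 4 or more contacts (half the patients): covariance with contacts = h(4 + 5 + 6 + 7)/8 − 3.5 × 0.5h = 2.75h − 1.75h = 1.0h. Expected slope = 1.0h/5.25 = 0.19h per contact. Squared correlation of line and step = 1.0²/(5.25 × 0.25) = 0.76.
- Step at 1 or more contacts (7/8 of patients): covariance = h(28/8 − 3.5 × 7/8) = 0.4375h. Expected slope = 0.4375h/5.25 = 0.083h. Squared correlation = 0.4375²/(5.25 × 0.1094) = 0.33.

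So a step of 1.0 point at 4 contacts gives the same expected slope as a straight line of 0.19 points per contact. Over all cuts from 1 to 7 the squared correlation runs from 0.33 to 0.76, so any step produces a non-zero expected slope. Neither the slope nor its p-value identifies the shape or a minimum number.

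**3. What a departure test could deliver.** The plan gives no power figure for Aim 3. Inputs from Power and Sample Size Considerations are 337 patients per arm at six months and a spread of 1.9. The text calls 1.9 a variance, so I checked it against the Aim 1 statement that "we will be able to detect a clinically meaningful difference in HbA1c across arms of" at least 0.43 with 80% power:
- 1.9 as an SD: (1.960 + 0.842) × 1.9 × √(2/337) = 0.41.
- 1.9 as a variance: (1.960 + 0.842) × √1.9 × √(2/337) = 0.30.

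The SD reading is nearer and is used here. Everything else is assumed: residual SD 1.6 after baseline adjustment, the six contacts scheduled before month 6, 60% of contacts reached at the centre of the distribution, and between-patient log-odds SD of 0 to 1.5 (0 and 1.0 for the cuts other than 4). The simulated test compares contacts as categories with a straight line, at the 5% level.

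| Step of 0.6 points at | Power of departure test |
|---|---|
| 2 contacts | 12–22% |
| 4 contacts | 22–27% |
| 5 contacts | 28–30% |
| 6 contacts | 14–24% |

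For a step at 4 contacts, power is 12–16% if the step is 0.43 points and 56–70% if it is 1.0 point. When the truth is a straight line, the test rejects in 4.7–5.0% of runs, as it should.

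**The case against.** **The wording does not force a straight line.** A linear model is linear in its coefficients, the Aim 1 model it refers to enters its exposure as an indicator, and the Aim 3 paragraph does not say how contacts or minutes are coded. Categories would be consistent with it. This stands. A reader might infer that the plan admits only a straight-line dose term, and the documents do not go that far. What they support is that no shape analysis is named for dose and that a slope is the natural reading.

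**There is partial cover elsewhere.** Checking assumptions could include checking linearity, and the exploratory higher-order terms could be applied to dose. That is possible, but neither sentence mentions dose and neither amounts to a threshold analysis fixed in advance.

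**Little is at stake and the remedy is weak.** Aim 3 has no numbered hypothesis, is worded as an investigation, is non-randomised within one arm, and would often stay unresolved even with a departure test. This limits the weight of the point. It does not remove it: Aim 3 is in the list of primary aims, and low power is a reason to state beforehand what a non-significant result means.

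**Further inferences that the documents do not support.**
- That a true threshold would usually make the slope significant. This depends strongly on where the step lies, so no general frequency can be given.
- That a quadratic term is useless. It is weak mainly against a central step; elsewhere it performs much like categories.
- That contact counts are distorted by feedback from HbA1c. Coaches do receive the value before a counselling session, but every intervention patient has the same schedule and no passage makes the number of contacts depend on HbA1c.

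**Conclusion.** The point holds as a gap between an aim and its analysis. On the natural reading, the Aim 3 model yields an association between amount of contact and outcome, and leaves open both the threshold-or-gradient question and the minimum number. It also replaces action plans with contacts and contact time without saying so. These conclusions rest on the text alone.

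The equal-slope example in step 2 is exact given an even spread of contacts, which is assumed. The power range in step 3 is illustrative, because the documents give no contact distribution, no residual SD and no expected dose effect.

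The plan should be amended, but the consequence is confined to Aim 3. The randomised comparison of HbA1c at six months does not use the dose variables.

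**What to change.** In the Aim 3 paragraph of Data Analysis:
- Pre-specify one dose-shape analysis in the ACP arm: number of contacts in categories fixed in advance, or a spline or change-point term in dose, with a test of departure from a straight line.
- Report any cut-point with its interval.
- State that a non-significant departure test does not establish a gradient.
- Say whether contacts stand in for action plans or whether action plans will be counted.
- Describe the results as associations, because the amount of coaching is not randomised.

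The cost is a few sentences and some extra analysis, with no change to design, sample size or patient contact. The tracking system described under Preparation phase and the coach logs under Fidelity outcomes already record contacts and their length. A count of action plans might need abstraction from the monthly EHR care notes. The main drawback is the limited power shown above: the honest result may be that the shape could not be determined.
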